7.1 Expected duration of participation and description of the trial timeline

Study duration estimated at 28 months

Study start date (first patient included): 6 May 2021

End date (end of follow-up of the last patient in the study): September 2023

Total duration of patient participation in the study: 3 months maximum.

The date of completion of the study will be sent to the competent authority and the CPP within 90 days.

If the study is stopped prematurely, information will be sent to the competent authority and the CPP within 15 days.

7.2 Description of procedures performed on individuals (description of each visit)

7.2.1 Physiotherapy group (Group 1)

The masso-physiotherapy procedures recommended by the HAS (2005) and in accordance with the Nomenclature Générale des Actes Professionnels (NGAP) for the treatment of low back pain are as follows:

- physical exercise,
- massage,
- electrotherapy,
- spinal traction,
- adjuvant treatments (balneotherapy, cryotherapy, etc).

The choice of procedures and their combination is left to the discretion of the practitioner according to his initial assessment, the needs and possibilities of the patient and his therapeutic preferences (in accordance with the principles of EBM).

In this study, practitioners are encouraged to keep to the usual session time of between 30 and 45 minutes.

7.2.2 Masso-physiotherapy and fasciatherapy group (Group 2)

Practitioners carry out both masso-physiotherapy and fasciatherapy procedures at each session. The time devoted to each of these acts, and the order in which they are performed, is left to the discretion of the practitioners, depending on their assessment and clinical progress.

The length of sessions observed (Courraud, 2015) is 30 to 45 minutes. Participating practitioners will be encouraged to respect this time.

7.2.3 Fasciatherapy group (Group 3)

Practitioners only carry out fasciatherapy procedures using manual (myofascial, articular, visceral) and/or gestural treatment techniques. The choice of procedures, their order of application and their combination is left to the discretion of the practitioners, depending on their assessment and the patient's clinical progress.

The length of sessions observed (Courraud, 2015) is 30 to 45 minutes. Participating practitioners will be encouraged to respect this time.

The fasciatherapy techniques used in this study are 'non-manipulative' (i.e. no forced manipulation of joints or soft tissues), manual and gestural (no use of instruments or adjuvant products) and aim to restore the mechanical properties of the fascias (sliding, elasticity, mobility) in order to restore their function (continuity, contractility, sensitivity). The maneuvers are performed very slowly (with each stretch lasting about 15 seconds), resulting in a gradual and global stretching of the fascia in the

lumbar region and its distant connections. During this stretching, the practitioner establishes a support point (holding the stretched fascia) to alter the fascial tone. The practitioner evaluates areas of tension and tightness in the lumbar fascia to guide the treatment plan and identify the specific areas to address.

7.3 Description of the general logistical organisation of the trial

Practitioners will receive an observation booklet by post. Each practitioner will include between 3 and 5 patients in the study.

The promoter is responsible for gathering all the data collected at each phase of the study and at the end of the study. They will compile the data into an Excel file and transmit it to the statistician.

- 7.4 Inclusion criteria for practitioners
 - Qualified physiotherapist,
 - Private practice,
 - Having a mixed practice combining conventional physiotherapy and fasciatherapy which is outside the scope of conventional practice,
 - Having completed at least 105 hours of training in fasciatherapy.

8 Data collected

8.1 Source data

8.1.1 Definition

Source documents, defined as any original document or object making it possible to prove the existence or accuracy of data or facts recorded during the clinical study, will be kept for 15 years by FasciaFrance.

8.1.2 Observation booklet and investigator's brochure

Investigator brochure :

- Cover page mentioning "Investigator Brochure"
- Investigator instruction sheet
- General overview of the study
- Investigator memo: "What to do and when for each patient?"
- Filling instructions
- CV and characteristics sheet of the investigator physiotherapist
- Correspondence table
- A copy of the self-administered questionnaires

Observation book :

- Cover page mentioning "Observation Notebook"
- Patient eligibility sheet (inclusion and exclusion criteria)
- Patient dividers and temporal dividers for the investigator's reference
- Patient information form
- Patient consent form in two copies
- Administrative and medico-social patient sheet
- Anonymized evaluation questionnaires and the Visual Analog Scale (VAS) sheet, distributed according to the study protocol

- Patient follow-up sheet (dates, session description, medications, significant events), divided into five sections
- Serious Adverse Event (SAE) reporting sheet

8.2 Collection of personal data

8.2.1 Origin and nature

Age, sex, living environment, family situation, professional situation, duration of low back pain in months, treatments received, current treatments, leisure activities, sick leave.

8.2.2 Justification for using them

The data collected enables us to check that a patient is not included twice in the study.

8.3 Data circulation

8.3.1 Data capture and processing

The source data will be collected by the investigators and private practitioners, and collated by the investigators. The data will then be entered into the database in ACCESS format.

The people :

- 1. who will be responsible for implementing automated data processing: [name], [name] data processors;
- 2. who will have access to the data: [name], [name] and [name], in charge of data entry

The data entry control procedure consists of a double reading of the data by the principal and secondary investigators, who certify on their honour that they have entered the data honestly as collected.

8.3.2 Data export / Multicentre study

Anonymised data will be collected by the physiotherapists, placed in an envelope and sent by post to the promoter FasciaFrance, [name].

8.3.3 Confidentiality

In accordance with the provisions concerning the confidentiality of data to which the persons responsible for quality control of research involving the human person have access (article L.1121-3 of the Public Health Code).

These people, in the same way as the investigators themselves, are subject to professional secrecy (under the conditions defined by articles 226-13 and 226-14 of the French Penal Code).

During the research or at its conclusion, the data collected on the persons involved and transmitted to the sponsor by the investigators (or any other specialist) will be rendered anonymous. Under no circumstances must the names or addresses of the persons concerned appear in clear text.

The co-ordinating investigator will ensure that each person taking part in the research has given written consent for access to their personal data, which is strictly necessary for the quality control of the research.

Anonymity is ensured by means of a correspondence table supplied to the investigator, filled in and kept by him alone. This correspondence table assigns a coded, completely anonymous identifier to each patient.

8.3.4 Archiving

The following documents will be archived by the name of the study at the FasciaFrance premises, under the responsibility of the coordinating investigator and FasciaFrance for 15 years after the end of the study.

These documents are :

- Protocol, observation book, any amendments,
- Original signed information forms and consents
- Individual data (authenticated copies of raw data)
- Follow-up documents
- Statistical analysis
- Final study report

At the end of the period of practical use, all documents to be archived will be placed under the responsibility of FasciaFrance.

No removal or destruction may be carried out without the agreement of the Developer. At the end of the 15 years, the Promoter will be consulted for destruction. All data, documents and reports may be subject to audit or inspection.

9 Statistical considerations

- 9.1 Data analysis method
 - 9.1.1 General

Statistical analysis will be carried out using Stata software (version 15, StataCorp, College Station).

Continuous variables will be presented in the form of mean and standard deviation, subject to the normality of their distribution (Shapiro-Wilk test if necessary). In the event of non-normality, they will be presented in the form of median, quartiles and extreme values. Qualitative variables should be expressed in terms of numbers and associated percentages. Wherever possible, graphical representations should be associated with these analyses.

Patients will be described and compared between groups (group receiving conventional physiotherapy only, group receiving both conventional physiotherapy and fasciatherapy and group receiving fasciatherapy only) at inclusion according to the following variables: compliance with eligibility criteria, epidemiological characteristics, clinical characteristics and characteristics of any treatments.

A description of protocol deviations, patients allocated according to these deviations and reasons for drop-out will also be provided. The number of patients included and the inclusion curve will be presented by randomisation group.

The initial comparability of the groups will be assessed on the main characteristics of the participants and potential factors associated with the primary endpoint. Any difference between groups on any of these characteristics will be determined on the basis of clinical and not just statistical considerations.

Comparisons between randomisation groups will be made systematically (1) without adjustment (2) by adjusting for factors whose distribution could be unbalanced between groups.

All statistical tests will be carried out with a risk of error of the first kind α of 5%.

Part of the analyses concerning the secondary evaluation criteria should be mainly exploratory in nature. As discussed by several authors (*Bender, R.; Lange, S. Adjusting for multiple testing-When and how? J. Clin. Epidemiol. 2001, 54, 343-349; Feise, R.J. Do multiple outcome measures require p-value adjustment? BMC Med. Res. Methodol. 2002, 2, 8; Rothman, K.J. No adjustments are needed for multiple comparisons. Epidemiology 1990, 1, 43-46*), adjustment for the risk of error of 1st kind will not be proposed systematically, but on a case-by-case basis in the light of clinical and not purely statistical considerations.

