9.1.2 Main analysis

In order to evaluate the specific benefits of fasciatherapy compared with physiotherapy for chronic low back pain in terms of variation in pain before and after each of the 5 sessions considered in this protocol, the main analysis will consider a mixed model approach for repeated data, making it possible to study the fixed group effects (group receiving only conventional physiotherapy, group receiving both conventional physiotherapy and fasciatherapy and group receiving fasciatherapy only), assessment time (session) and their interaction, while taking into account inter- and intrapatient variability (subject taken as a random effect), in addition to the (random) practitioner effect. The results will be expressed in terms of regression coefficient and 95% confidence interval. It will also be proposed to study the difference between randomisation groups for each of the sessions. The results will be expressed in terms of effect size and 95% confidence interval.

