9.1.4 Method for taking into account missing, unused or invalid data

A sensitivity analysis will be carried out to study the attrition bias, i.e. the quantity (level of attrition) and nature (independence from the randomisation group) of the missing data, and to propose the most appropriate data imputation method if necessary.

9.2 Justification of the number of subjects / power analysis.

In order to evaluate the specific benefits of fasciatherapy compared with physiotherapy for chronic low back pain in terms of variation in pain before and after each of the 5 sessions considered in this protocol, the estimate of numbers is based on recruitment capacity, the time required for experimentation and simulations concerning the effect size for risks of error of 1st and 2nd kind fixed respectively at 1.7% (two-sided with correction for multiple comparisons: group receiving only conventional physiotherapy, group receiving conventional physiotherapy and fasciatherapy) and less than 20%.

Thus, if we estimate that a clinically relevant difference in pain assessment is between 1 and 2 points, for a standard deviation of the variation in pain of 1.5 to 2.5 points, we should include 30 to 40 patients for a statistical power of over 80% and an intra-individual correlation coefficient (5 sessions per subject) conventionally set at 0.5.

This proposal must be revised upwards in order to take into account the dropouts inherent in this type of protocol and the inter- and intra-practitioner variability (due to the experimental design of the cluster trial) which can be measured by the intra-class correlation coefficient and which it seems reasonable to estimate in the context of this project to be of the order of 0.05 to 0.2. It is therefore proposed to include 60 patients in each of the study groups.

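### The trial is sized at a two-sided 1.7% corrected for multiple comparisons, but the analysis section tests everything at 5% and never carries the correction into the primary comparison

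*Combined protocol and SAP*

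**What the plan says.** - **Section 9.2 (number of subjects):** the type I and type II risks are "fixed respectively at 1.7% (two-sided with correction for multiple comparisons", and the bracket goes on "group receiving only conventional physiotherapy, group receiving conventional physiotherapy and fasciatherapy) and less than 20" per cent. The 1.7% is the type I risk; the figure after the bracket is the type II risk. The bracket names two groups, not a list of comparisons.
- **Section 9.1.1 (general rules):** "All statistical tests will be carried out with a risk of error of the first kind α of 5" per cent. The next paragraph leaves multiplicity adjustment to a case-by-case decision, but it opens "Part of the analyses concerning the secondary evaluation criteria should be mainly exploratory in nature", so it concerns the secondary criteria.
- **Section 9.1.2 (main analysis):** a mixed model with group (three levels), session and their interaction, and random patient and practitioner effects. "The results will be expressed in terms of regression coefficient and 95% confidence interval". It adds: "It will also be proposed to study the difference between randomisation groups for each of the sessions". It gives no corrected level, no gatekeeping test and no named primary contrast.
- **Link between the two:** 9.1.2 and 9.2 both begin "In order to evaluate the specific benefits of fasciatherapy compared with physiotherapy for chronic low back pain", so the 1.7% was set for the main analysis.
- **Section 3.1 (main objective):** covers fasciatherapy both alone and combined with physiotherapy, so at least two contrasts with physiotherapy are implied.
- **Section 9.3:** mentions a statistical analysis plan in the study file that may be revised during the study.

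**The concern.** One primary question has two type I error levels. The sizing counts on a correction for three comparisons; the analysis rules do not apply it. A primary contrast with p = 0.03 would pass the level in 9.1.1 and miss the level assumed in 9.2. Nothing fixes in advance which applies, so the choice could be made after the results are seen. With three arms and at least two contrasts of interest, this bears directly on whether fasciatherapy is declared superior to physiotherapy.

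**Working it through.** **The plan's own figure.** Bonferroni for three comparisons gives 0.05/3 = 0.0167; Šidák gives 1 − 0.95^(1/3) = 0.01695. Both round to the stated 1.7%. Two comparisons would give 2.5% under Bonferroni, so 1.7% corresponds to all three pairs.

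**Family-wise error when no group differs** (three equal arms, one test per contrast, no gate). The critical values are z = 1.960 at 5% and z = 2.394 at 0.05/3. For all three pairs the error is P(Q > z√2), with Q the studentised range of three means. For two contrasts sharing the physiotherapy arm it is the two-sided exceedance of a bivariate normal with correlation 0.5.

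| Family | Each at 5% | Each at 0.05/3 | Difference |
|---|---|---|---|
| Two contrasts with physiotherapy | 9.07% | 3.13% | 5.9 points |
| All three pairs | 12.23% | 4.40% | 7.8 points |

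The last column is the chance, when no group differs, that the smallest p-value lies between 0.0167 and 0.05, so that the two sections disagree.

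- *Small number of practitioners.* With 60 patients per arm and 3 to 5 per practitioner (section 7.3), there are 12 to 20 practitioners per arm, or 33 to 57 degrees of freedom. The three-pair error at 5% is then 12.0% to 12.1%.
- *With a gate.* If a 5% global group test had to be significant first, simulation gives 5.0%. No such test is stated.
- *Session-by-session tests.* The figures cover one test per contrast. Separate tests at each of five sessions would raise them.

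**Power given up by using 0.05/3.** Inputs from section 9.2: within-patient correlation 0.5 over five sessions, SD 1.5 to 2.5, practitioner ICC 0.05 to 0.2, 60 per arm. For a contrast averaged over sessions, with m patients per practitioner:

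variance of a group mean = SD² × [(1 + 4 × 0.5)/5 + (m − 1) × ICC] / n; SE = √(2 × variance).

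Base case SD 2, m = 4, ICC 0.1, n = 60: variance = 4 × (0.6 + 0.3)/60 = 0.06, SE = √0.12 = 0.346. For a 1-point difference, 1/0.346 = 2.887. Power at 5% = Φ(2.887 − 1.960) = 0.823; at 0.05/3 = Φ(2.887 − 2.394) = 0.689. The gap, 13 points, is the chance that such a true difference gives a p-value on which the two sections disagree.

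| Scenario (SD 2, ICC 0.1) | 5% | 0.05/3 |
|---|---|---|
| 1.5 points, n = 60, m = 4 | 99% | 97% |
| 1 point, n = 60, m = 4 | 82% | 69% |
| 1 point, assumed 20% dropout (n = 48, m = 3.2) | 77% | 62% |
| 1 point, single session, n = 60, m = 4 | 67% | 50% |

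Holm over three pairs gives 72% per contrast with physiotherapy when both fasciatherapy arms differ from it by 1 point (simulation).

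Across the plan's ranges (SD 1.5, 2, 2.5; m 3, 4, 5; ICC 0.05, 0.1, 0.2; 27 combinations), the number with power below 80% is:

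| Difference | At 5% | At 0.05/3 |
|---|---|---|
| 1 point | 13 | 18 |
| 1.5 points | 1 | 2 |
| 2 points | 0 | 0 |

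The lowest value at 0.05/3 is 29% (1 point, SD 2.5, m = 5, ICC 0.2), where testing at 5% gives 46%.

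**The case against.** The best defence is that the two figures are compatible: 5% is the overall risk and 1.7% the per-comparison level that delivers it. That may well be the intent. But 9.1.1 applies 5% to every test, not to the family, and 9.1.2 says nothing to the contrary. If this is the intent, the fix simply records it.

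Other points have some force:

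- **Sizing is not a decision rule.** True, and sizing at a stricter level than the test level is not invalid in itself. But 9.2 describes its level as a correction for multiple comparisons, and that correction exists only if the analysis applies it.
- **95% intervals prove little.** Unadjusted intervals can accompany adjusted tests. The point rests mainly on the 5% sentence and the silence of 9.1.2.
- **A global test may be intended.** With exactly three groups, a 5% global test followed by 5% pairwise tests is valid. In the base case, with both fasciatherapy arms 1 point from physiotherapy, its power per contrast is about 78%, better than 0.05/3 or Holm. It is a legitimate alternative, but it has to be written down. The 9% to 12% figures hold only without it.
- **The power figures are approximate.** Section 9.2 does not say on which scale the practitioner ICC applies. If it applies to a patient's five-session mean, the 1-point base case is 87% at 5% and 76% at 0.05/3, the minimum at 0.05/3 is 39%, and the 1-point counts below 80% are 11 and 16. On the scale used above, a t-test on 42 degrees of freedom gives 81% and 65%. The cost of the fix shifts; the inconsistency does not.
- **The separate analysis plan may settle it.** Possibly, but the text provided does not.

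**Conclusion.** The concern holds. The stated testing rule is weaker than the error control on which the trial was sized, and the case-by-case sentence does not close the gap because it belongs to the secondary criteria. Tested at 5% without a gate, the primary family carries a 9.1% (two contrasts) to 12.2% (three pairs) chance of a false claim, against 3.1% to 4.4% at 0.05/3. This assumes balanced arms, no true difference and one test per contrast. It should be corrected before any between-group result is seen, because it decides how a primary p-value between 0.017 and 0.05 is read.

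**What to change.** 1. **Section 9.1.1:** change the general rule to *two-sided 5%, except the primary group contrasts (see 9.1.2)*.
2. **Section 9.1.2:** name the primary pairwise contrasts from the mixed model (the difference averaged over the five sessions is one option) and test each at 0.05/3 with a 98.3% interval. Holm is acceptable for the decisions; the 98.3% intervals are then conservative and can include zero when Holm rejects. Label the session-by-session differences as supportive.
3. **Section 9.2:** make the bracket list the comparisons that the 1.7% covers. The level 0.05/3 matches all three pairs. It still controls the error if only the two contrasts with physiotherapy are kept, although 2.5% each would then suffice (74% power in the 1-point base case).

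If the sponsor prefers a 5% global group test as a gate, 9.1.2 should say so and 9.2 should be brought into line with it.

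The change is wording only, with no new data or patients. The cost is a stricter threshold than 5%, with the power losses shown above. On those figures, 60 per arm supports the 1.7% level for differences of 1.5 to 2 points in most combinations of the plan's assumptions, but not reliably for 1 point. Section 9.2 should say so.

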9.1.2 Main analysis

In order to evaluate the specific benefits of fasciatherapy compared with physiotherapy for chronic low back pain in terms of variation in pain before and after each of the 5 sessions considered in this protocol, the main analysis will consider a mixed model approach for repeated data, making it possible to study the fixed group effects (group receiving only conventional physiotherapy, group receiving both conventional physiotherapy and fasciatherapy and group receiving fasciatherapy only), assessment time (session) and their interaction, while taking into account inter- and intrapatient variability (subject taken as a random effect), in addition to the (random) practitioner effect. The results will be expressed in terms of regression coefficient and 95% confidence interval. It will also be proposed to study the difference between randomisation groups for each of the sessions. The results will be expressed in terms of effect size and 95% confidence interval.

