6.1 Assessment criteria

6.1.1 Primary endpoint

The main evaluation criterion will be pain, measured using the VAS (visual analogue evaluation) scale (Moquet 1999) to assess pain levels, before and after each session.

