6.2 Investigation method used

This is a cluster randomised clinical trial.

The methodology is pragmatic:

- Patients with common chronic low back pain were included, regardless of co-morbidities,
- The comparative intervention is physiotherapy,

- The instructions for implementing the experimental or control intervention are flexible, leaving the practitioner considerable latitude in the application of the intervention,
- The experimental and control intervention is deployed under all clinical conditions, with attention paid only to the dose delivered and to side effects,
- There is no follow-up of patients after the end of the study.

Three groups of low back pain patients will be selected:

- A group receiving only conventional physiotherapy;
- A group receiving both conventional masso-physiotherapy and fasciatherapy treatments;
- A group receiving fasciatherapy treatments only.

All patients will receive 5 sessions over a maximum period of 3 months. The frequency of the sessions will be determined by the practitioner, and the duration of each session may vary from 30 to 45 minutes in order to respect the usual ways of practising masso-physiotherapy and fasciatherapy. The study will be limited to 5 sessions because a previous survey of physiotherapists practising fasciatherapy showed that they carried out an average of 5 fasciatherapy sessions for the treatment of a patient with low back pain. In order to be able to compare the groups, we decided to use this number of sessions. As the number of physiotherapy sessions was defined by each physiotherapist following the physiotherapy assessment, there was a risk of differences in the number of sessions between the groups and between practitioners in the same group. For this reason, we also chose to limit the study to 5 sessions. However, patients will of course be able to continue with the sessions if this proves necessary.

The choice of specific techniques used by the practitioner is left to his or her discretion, whether for physiotherapy (massage, physiotherapy, exercises, etc.) or fasciatherapy (manual therapy, exercise, etc.).

The only additional procedures compared with ordinary care are the secondary assessment questionnaires.

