9.1.3 Secondary analyses

The analyses described above for the primary endpoint will be supplemented in a multivariate situation by a mixed linear regression model to take into account the covariates selected on the basis of the results of the univariate analysis and their clinical relevance. The practitioner effect will be measured and taken into account in the statistical analyses as a random effect. The results will be expressed in terms of regression coefficient and 95% confidence interval.

Comparisons between randomisation groups (group receiving only conventional massophysiotherapy, group receiving both conventional masso-physiotherapy and fasciatherapy and group receiving only fasciatherapy) concerning quantitative assessment criteria (functional assessment by the DALLAS self-assessment questionnaire, quality of life assessment by the SF-12 quality of life questionnaire, psychological assessment by the STAI Y questionnaire) will be carried out by Student's t-test or non-parametric Mann-Whitney test if the test conditions are met, assessment of quality of life using the SF-12 quality of life questionnaire, psychological assessment using the STAI Y questionnaire) will be carried out using Student's t test or the non-parametric Mann-Whitney test if the conditions of Student's test are not met (normality verified by the Shapiro-Wilk test and equality of variances by the Fisher-Snedecor test). Particular attention will be paid to the statistical distributions of the quantitative data under study. Where appropriate, the above analyses may be supplemented by more appropriate generalised linear regressions. The results will be expressed in terms of effect size and 95% confidence interval. In line with the recommendations proposed by Vickers and Altman, an ANCOVA-type analysis will also be proposed in order to compare the scores at the 5th session by adjusting for the values at the 1st session.

The STAI YB measuring anxiety status will be completed at the beginning and end of each session; the statistical analysis will therefore follow the same statistical analysis plan as that described for the primary endpoint.

Comparisons between the randomisation groups (conventional physiotherapy-only group, conventional physiotherapy and fasciatherapy group and fasciatherapy-only group) for categorical variables (e.g. functional assessment scores, quality of life assessment scores and psychological

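### Section 9.1.2 does not say how patient and practitioner effects may vary over the five sessions; fitted as random intercepts, the group-by-session tests can be too liberal

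*Combined protocol and SAP*

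**What the plan says.** Section 9.1.2 plans a mixed model for repeated data with fixed effects for group, "assessment time (session) and their interaction", and describes the random part as "while taking into account inter- and intrapatient variability (subject taken as a random effect), in addition to the (random) practitioner effect". It then adds: "It will also be proposed to study the difference between randomisation groups for each of the sessions". Section 9.1.3 repeats the practitioner term: "The practitioner effect will be measured and taken into account in the statistical analyses as a random effect". For the state-anxiety score completed at every session it says that "the statistical analysis will therefore follow the same statistical analysis plan as that described for the primary endpoint".

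No random slope, within-patient covariance pattern, practitioner-by-session term, robust variance or degrees-of-freedom method is named. The sample-size text in section 9.2 uses one correlation for all pairs of sessions: "an intra-individual correlation coefficient (5 sessions per subject) conventionally set at 0.5". Section 6.3 makes practitioners the randomised units. Section 6.2 leaves techniques to their discretion and also states: "The frequency of the sessions will be determined by the practitioner".

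**The concern.** An unqualified random effect is normally fitted as a random intercept. Two intercepts plus an independent residual give compound symmetry: the same variance at every session, and the same correlation between sessions 1 and 2 as between sessions 1 and 5. The practitioner intercept then drops out of any contrast between sessions. Group-by-session is judged against a residual that treats patients of the same practitioner as independent in how they change. Given the latitude in section 6.2, practitioner-specific time courses are plausible.

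At stake are the interaction test and the between-session contrasts, both part of the main analysis, and the same results for state anxiety. An apparent divergence of the arms over the course could carry more than the stated 5% error.

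**Working it through.** **The plan's own figure.** Section 9.2 arrives at 30 to 40 patients per group, then 60. With two-sided alpha 1.7% and power 80%, (z₁ + z₂)² = 3.228² = 10.42. For the mean of five sessions with one constant correlation of 0.5, the variance factor is (1 + 4 × 0.5)/5 = 0.6.
- Difference 1, SD 1.5: n = 2 × 1.5² × 10.42 × 0.6 = 28.1, so 29.
- Difference 1.5, SD 2.5: n = 2 × (2.5/1.5)² × 10.42 × 0.6 = 34.7, so 35.

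The stated 30 to 40 is therefore compatible with constant correlation, though the plan's full input ranges give 8 to 79. This fits the random-intercept reading but does not prove it.

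**Inputs for the check.** From the documents: three groups of 60, five sessions, 3 to 5 patients per practitioner (section 7.3), practitioner ICC 0.05 to 0.2 (section 9.2), alpha 5% (section 9.1.1). Assumed: 12 practitioners × 5 patients per group; AR(1) correlation 0.7; practitioner share 0.10 or 0.20; and, in the drift cases, a practitioner effect that follows the same AR(1) pattern. The documents give no variance that changes over sessions.

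**Closed form, session 5 versus 1.** The mean pairwise AR(1) correlation is (4 × 0.7 + 3 × 0.49 + 2 × 0.343 + 0.2401)/10 = 0.52, close to the plan's 0.5. In units of the common variance:
- true variance of the difference: 2 × (1 − 0.7⁴) = 1.520
- variance the intercept model uses: 2 × (1 − 0.5196) = 0.961
- SE ratio: √(1.520/0.961) = 1.26
- type I error: 2 × [1 − Φ(1.96/1.26)] = 12%

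If the practitioner effect also drifts, the true variance is multiplied by 1 + (m − 1) × share. With m = 5 this is 1.4 at share 0.10 and 1.8 at share 0.20. The SE ratios become 1.26 × √1.4 = 1.49 and 1.26 × √1.8 = 1.69, and the type I errors 19% and 25%.

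**Simulation under no group effect.** The interaction has (3 − 1) × (5 − 1) = 8 df. Type I error of the random-intercept model at nominal 5%:

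| True structure | 8-df interaction | Session 5 v 1 |
|---|---|---|
| Constant correlation | about 5–6% | not inflated |
| AR(1), practitioner effect constant | about 6–8% | 12% |
| AR(1) with practitioner drift, share 0.10 | about 20% (19–22%) | 18–19% |
| AR(1) with practitioner drift, share 0.20 | about 37% | 25% |

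With drift at share 0.05, the interaction error is 11% with 3 patients per practitioner and 14% with 5.

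**Other mechanisms.** A second simulation used 15 practitioners × 4 patients per group, session-1 SD 2.0, correlation 0.5, ICC 0.1 and 20,000 runs per case:

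| True structure | Interaction | Session 1 difference | Session 5 difference | Average over sessions |
|---|---|---|---|---|
| Constant correlation | 5.1% | 5.2% | 5.1% | 5.6% |
| AR(1) only | 7.2% | 5.0% | 5.3% | 5.5% |
| Patient slope SD 0.5 per session | 5.8% | 2.8% | 10.0% | 5.7% |
| Practitioner slope SD 0.3 | 16.6% | 2.9% | 12.7% | 5.7% |
| Independent practitioner-by-session variance, 10% of total | 29.3% | 7.3% | 7.6% | 5.6% |

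Single-session differences are almost untouched by AR(1) decay. They go wrong mainly when spread or slopes change over sessions.

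**Does the remedy work?** An unstructured within-patient covariance plus a practitioner-by-session effect was fitted in the 3 × 12 × 5 × 5 design, 500 runs per case (Monte Carlo SE about 1 percentage point at 5%). With a plain Wald test the interaction error was about 5% under constant correlation or AR(1), and 9–12% under drift. With a small-sample F it was 2–6%. In the second design, practitioner-level means with t or Hotelling tests held 4.6–5.4% in every scenario. Practitioner-clustered standard errors without a small-sample correction were themselves liberal: 12% or more, and about 25% for the 8-df chi-square test in one simulation.

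**The case against.** The text never says constant, intercept or compound symmetry, and section 9.3 mentions a statistical analysis plan kept in the study file that may say more. A reader might infer that the error bars are wrong. The documents do not support that: the structure is unspecified, and under constant correlation the intercept model is correct. This stands, and it makes the point conditional.

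The outcome also matters. Pain is recorded "to assess pain levels, before and after each session", and section 9.1.2 speaks of variation around each session. If the response is the within-session change, much of the slowly drifting pain level is differenced out and constant correlation may be nearer the truth. This weakens the AR(1) case. It does not answer the practitioner case, because practitioners may also differ in how within-session change evolves.

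A reader might also treat the 1.5 to 2.5 SD range in section 9.2 as a decline over the sessions and derive poor interval coverage from it. That range is a planning range for the SD of the variation in pain, not a time course, so it supports no such figure.

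Finally, the larger error rates depend on assumed drift. The plan's ICC of 0.05 to 0.2 describes overall clustering, not change over sessions. This also stands; without drift or practitioner-by-session variation, the joint interaction test is only mildly affected.

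**Conclusion.** The point holds as a conditional weakness of specification in the main analysis. Fitted in the natural way, the model ignores practitioner-level variation over sessions in a trial that randomises practitioners. Under the assumed covariances the interaction test runs at about 6–8% with decay alone and about 20% to 37% with practitioner drift; session 5 versus 1 runs at 12–25%.

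Two stronger readings are not supported. The first is that a false finding of divergence is to be expected: no input in the documents fixes the size of any drift, and even the largest simulated interaction rate is well below one half. The second is that the overall comparison of the arms is compromised: the group effect averaged over sessions stayed at 5.2–5.8% in every scenario with complete, balanced data.

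The number of practitioners is a further assumption. Twelve per group is 36, within the 41 reported as able to recruit in section 11.4; fifteen per group is 45, which exceeds it. Fewer practitioners would make a small-sample correction more important.

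**What to change.** In section 9.1.2, and explicitly for state anxiety in section 9.1.3:
- Replace the single patient intercept with an unstructured covariance over the five sessions.
- Keep the practitioner intercept and add a practitioner-by-session random effect, or a practitioner slope.
- Name a small-sample degrees-of-freedom correction, such as Kenward-Roger.
- State the fallback order for non-convergence in advance, for example heterogeneous Toeplitz, then AR(1), keeping the practitioner-by-session term where it can be estimated.
- Refer any check based on practitioner-clustered standard errors or practitioner-level means to a small-sample t or F distribution.

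The cost is SAP wording and a code change; data collection is unaffected. There are about 17 covariance parameters (15 within patient, 2 for practitioner) in place of 3, some risk of non-convergence, and slightly wider intervals. The small-sample F can be somewhat conservative, as the 2% at the lower end of its simulated range shows. Fixing the structure before analysis also removes a choice that would otherwise be made after seeing the data.
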